Given that all participants will be in a program designed to improve relationships and prevent IPA, the added risks are those associated with the research assessments. All participants will be encouraged to discuss any painful issues that arise during the initial assessment. Those who do not receive intervention will be provided with referrals for counseling during the assessments as well as information on safety and resources for victims of abuse, such as 24-hour hotline numbers and shelter/legal services information. All participants who complete the *Supportive Prevention* group intervention will also have the option to participate in the *Strength at Home-Couples'* intervention.

A second risk involves the possibility that material discussed during assessments will become the topic of a violent conflict. To minimize this risk, all assessments will be conducted separately with partners.

All identifying information (e.g., signed consent forms) will be stored separately from the research questionnaires. Separate locked, secure files will be used to store study materials for each participant, and couple's files will be kept in separate storage areas to ensure confidentiality and safety. Identity masking subject numbers assigned to each participant will be the only means by which collected information is labeled. Each participant will have his or her own assigned number. Subject numbers will reflect the link between participating members of the couple. The only list that will link the names of the participants with their subject numbers will be kept in a secure, password-protected computer account accessible only to the on-site study staff. Study results will be presented and/or published in a fashion to ensure that participants cannot be identified.

Data collected through the REDCap system will be encrypted and unidentifiable to REDCap staff. It will be accessed only by the study staff at Joint Base Lewis-McChord and Boston VA Healthcare System.

(10) Potential Benefit of the Proposed Research to the Subject and Others

The risks associated with the project are deemed to be justified on several grounds. First, there may be benefits associated with the research assessment, particularly for those reporting relationship problems and potential IPA, who will have an opportunity to discuss their situation with a trained psychoeducational facilitator. The facilitator will be prepared to complete a safety plan with the victim, provide support, and give information about local hotlines and shelter/legal services. Second, all participants will be scheduled to receive a program designed to prevent aggressive behavior. Finally, the findings are likely to benefit others through the possible enhancement of relationships and prevention of IPA in the future.

(11) Importance of the Knowledge to be Gained

There is no currently available evidence-based intervention for military couples to prevent negative trajectories that may include IPV from developing after deployment or upon exposure to trauma. The *Strength at Home-Couples' (SAH-C)* program was designed to fill this gap in services and assist in preventing IPA in those couples who may be at risk for relationship problems. Through a recently completed randomized controlled trial funded by the Centers for Disease Control, we have shown *SAH-C* to be effective in preventing both physical and psychological IPV relative to those receiving a *Supportive Prevention* intervention among veterans and service members within the Department of Veterans Affairs. Before we disseminate *SAH-C* on a large scale on military installations, it would be important to examine its efficacy in this particular setting and to identify any potential barriers and facilitators for implementation. Potential short-term impacts from the current study would be to demonstrate best clinical practices in reducing IPV risk and preventing IPV in military dyads. Long term, study results could assist in changing the way we manage and prevent IPV, not only in military settings, but also beyond the military context since trauma is linked with violence in civilians in addition to military members.

(12) Resources

(a) Research Space

The Principal Investigator is a staff psychologist in the National Center for PTSD at the Boston VA Medical Center. He has an office and research lab space at the Jamaica Plain Campus of the Boston VA.

Study staff will be provided an office space and a conference room on Joint Base Lewis-McChord to recruit, assess participants, and hold groups.

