Based on Stakeholder Advisory Board recommendations and an examination of the pilot data, refinements will be made to the *SAH-C* manual. As a final working version becomes available, intervention integrity measures will be refined based on changes to the manual and psychoeducational intervention integrity ratings

(5) Phase 2: Randomized Trial/Pre-Implementation Phase

(a) Study Design

The refined intervention manual and integrity measures from Phase 1 will be tested in Phase 2 in a randomized trial. Figure 9 illustrates the study design, procedures, and schedule of assessments planned for Phase 2. This choice in study design is analogous to that used in our prior CDC trial within a VA setting and is consistent with recommendations about the appropriate progression of control conditions when determining the efficacy of any intervention.⁷³

Participants for Phase 2 will be 140 service members and their partners. The same recruitment procedures employed for Phase 1 will be used for Phase 2. Informed consent procedures will be almost identical to those described for Phase 1 in Section D.2.3., with the exceptions that they will be notified that they will participate in one of two possible interventions.

As in Phase 1, all assessments will remain confidential and will be stored separately from one another. Each assessment will also entail the provision of information regarding safety planning and IPA resources.

(b) Assignment to Groups

Random assignment will be completed after study enrollment using computer-generated random numbers. Assignment to conditions will be conducted using urn randomization methods to balance conditions on case severity. Urn randomization alters the probability of assignment to study conditions based on imbalances that resulted from prior random assignments.⁷⁴ This methodology allows for random assignment of each case, and maintains the possibility that each individual will be assigned to either condition, while at the same time reducing the chance of imbalances in prognostic factors that can threaten the validity of small-sample clinical trials.

(c) Interventions

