assumed to be a function of observed covariates and previously measured outcomes, but not unobserved outcomes). Based on such considerations, this type of an approach has been recommended for analyzing outcomes in prevention trials as it is generally more powerful than traditional repeated measures analyses of variance.⁹¹ In the current project it is of interest to model person-specific effects (i.e., time course for each participant), as well as the variation of responses between individuals. In addition, because of the suspected intraclass correlation between individuals nested within intervention groups, couples, and perhaps intervention site, these variables will be treated as fixed effects in the analyses. Time will be modeled as a random effect, and condition (*SAH-C* and *ST*) will be a fixed effect. Change in intervention outcomes over time and differences between the conditions over time (intervention by time interactions) will be examined. The primary effect size for the study will be derived from the random regression analyses, and specifically the intervention by time interaction, which will compare the two groups across intervention and follow ups. There are covariates that are *a priori* hypothesized to be associated with intervention outcomes, including socioeconomic status and education, and these will be included in follow-up analyses to significantly reduce error variance.

(e) Exploratory Analyses

Differences between the two group conditions in participant intervention compliance (Aim 2) will be explored by examining condition differences in session attendance using ANOVAs.

(f) Qualitative Analytic Strategy and Data Integration

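### Allocation is balanced on case severity, but the primary model contains neither that factor nor the baseline outcome score, so the condition-by-time contrast loses precision wherever either one predicts change

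*Combined protocol and SAP*

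**What the plan says.** Section (5)(b), Assignment to Groups: "Assignment to conditions will be conducted using urn randomization methods to balance conditions on case severity". The stated purpose is "reducing the chance of imbalances in prognostic factors that can threaten the validity of small-sample clinical trials". Case severity is given no instrument, cut-off or urn parameters anywhere in the document.

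Primary Data Analyses describes a random-effects regression: "Time will be modeled as a random effect, and condition (*SAH-C* and *ST*) will be a fixed effect". The primary effect size is "specifically the intervention by time interaction, which will compare the two groups across intervention and follow ups". The plan adds that "it is of interest to model person-specific effects (i.e., time course for each participant"), and it handles clustering by fixed effects: "individuals nested within intervention groups, couples, and perhaps intervention site, these variables will be treated as fixed effects in the analyses". No severity term and no baseline-score covariate are listed. The covariates expected in advance to predict outcome are described as "including socioeconomic status and education, and these will be included in follow-up analyses to significantly reduce error variance".

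The sponsor's previous randomised trial, reported under Preliminary Studies, did adjust: its six-month comparisons were ANCOVAs controlling for baseline scores.

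**The concern.** A factor judged prognostic enough to steer allocation would normally appear in the analysis. Balancing removes part of the chance variation between arms, but a model without the factor still counts that variation as error. The reported standard error is then larger than the true one, the interval is too wide and the test is conservative. Separately, a baseline score that predicts change can reduce residual variance whether or not it was used in allocation. The CTS-2, MMEA and DAS are all in the baseline battery, so the plan leaves this information unused in a trial of 140 couples. What is at stake is precision and a clear prespecification, not validity.

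**Working it through.** **Inputs from the documents.** Power Analysis gives a within-subject correlation r = .70 (observed range .53 to .90), d = .5, 20% attrition, 140 couples (280 individuals) and two-sided .05. Specific Objectives gives three assessments after baseline: post-intervention and two follow-ups.

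**Assumptions.** Variance is 1 and the correlation is equal across all four assessments. The contrast is the mean of the three later values minus baseline, compared between arms; the plan does not say whether time is linear or categorical. There is one composite per couple and no group clustering. The reported correlations are for CTS-2 aggression, so using them for relationship satisfaction is a further assumption.

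**1. The plan's own power figure.** Power = Φ(d / √(2v/n) − 1.96).
- Individuals: n = 140 × .8 = 112 per arm and v = 1. √(2/112) = .1336, .5/.1336 = 3.742, and Φ(1.782) = .963. This meets the stated figure of more than .9.
- Couples: n = 70 × .8 = 56 per arm, with the change contrast v = .40 (step 2). Power is .987.

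**2. Variance with and without baseline adjustment.**
- Unadjusted change: v = (1 + 2r)/3 + 1 − 2r
- Baseline-adjusted: v = (1 + 2r)/3 − r²

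| r | Unadjusted | Adjusted | Ratio | Interval narrower by |
|---|---|---|---|---|
| .53 | .627 | .406 | 1.54 | 20% |
| .70 | .800 + 1 − 1.400 = .400 | .800 − .490 = .310 | 1.29 | 1 − √(.310/.400) = 12% |
| .90 | .133 | .123 | 1.08 | 4% |

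The ratio is the equivalent increase in couples: 54%, 29% and 8%. At r = .70 and 56 couples per arm, power rises from .987 to .997.

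**3. Type I error under urn allocation.** This was simulated with 4,000 trials per scenario, 112 couples, r = .70, normal outcomes and an urn within severity strata.
- *Severity is the baseline score in two or four strata.* Without adjustment the type I error is .043 or .037, and the model standard error is about 3% to 6% too large. Adjusting for the strata narrows the interval from 0.473 to 0.438 or 0.427. Full baseline ANCOVA gives 0.417, which matches the 12% in step 2.
- *Severity is a trait with the same effect at every assessment, explaining 30% of variance.* Interval width is 0.473 against 0.474 and type I error is .047 against .048, so there is no excess to remove.

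**4. Why main effects do not help.** If severity adds the same amount γS to every assessment of a couple, then γS cancels in later-minus-baseline. In one simulated data set (112 couples, r = .70, complete data), the interaction standard error was .1167 with no covariates. It stayed at .1167 after adding severity, socioeconomic status and baseline as main effects. It fell to .1115 only when severity-by-time and baseline-by-time terms were added.

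**5. Physical IPA.** Inclusion criterion (c) requires both partners to report no physical IPA in the past 3 months, and the Phase 2 assessment window under Outcome Measures is also three months. The baseline score is therefore nearly constant and cannot correlate .70 with later values, so step 2 does not apply. Only a severity factor that predicts later physical IPA would reduce variance there.

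**The case against.** The strongest reply is that the primary effect is a within-person interaction. Person-level effects, and the couple fixed effects if read literally, already absorb any constant severity effect. This stands for a constant effect, and it is why entering severity as a main effect would achieve nothing. It does not stand where severity or baseline predicts change, and at any correlation below 1 the baseline score does predict change through regression to the mean.

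It is also fair that power for the change contrast is about .99 either way at d = .5, that keeping covariates for secondary models is common, and that the placement "these will be included in follow-up analyses to significantly reduce error variance" could refer to follow-up time points. The case for adjustment is therefore narrower intervals, not a rescue of power.

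A reader might infer several stronger points, which the documents do not support:
- **A type I error near 2.6%.** The formula 2(1 − Φ(1.96/√(1 − .225))) gives .026, where .225 = (.40 − .31)/.40. It assumes near-perfect balance on a continuous baseline score. The plan claims only a reduced chance of imbalance and never equates severity with that score.
- **Intervals too wide for every outcome.** Steps 3 and 5 show exceptions.
- **The larger loss of a comparison that ignores baseline** (simulated standard errors 15% to 21% too large, type I error .018 to .027). The hypotheses concern reductions over time and the primary effect is an interaction with time, which points to baseline being modelled, although the plan does not say so outright.
- **Bias or excess false positives.** The error runs the other way.

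**Conclusion.** The point holds as a specification gap with a measurable but conservative cost. The urn factor and the baseline score are both missing from the primary model. For psychological IPA, and by assumption for relationship satisfaction, baseline adjustment would narrow intervals by about 12% at r = .70, equal to about 29% more couples, with 54% to 8% over the plan's own range. The conservatism of the unadjusted test is mild (.037 to .043) if severity is strata of the baseline score, and absent if severity has only a time-constant effect. For physical IPA the baseline-score gain does not exist.

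The figures rest on equal variances and correlations, normal outcomes and no group clustering. Aggression counts are likely to be skewed, so the percentages are indicative. How much severity itself explains cannot be fixed, because the document neither defines it nor gives its association with outcome.

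**What to change.** Define case severity: the instrument, the cut-offs and the urn strata. State whether baseline is a modelled time point. Then prespecify one of these for the primary intention-to-treat model:

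1. Analyse the post-intervention and follow-up values, with the baseline outcome score and the urn factor as covariates.
2. Keep baseline in the outcome vector with a common mean across arms at baseline, and include urn-factor-by-time terms.

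Main effects of severity or baseline added to the present interaction model are not enough. Both options need couples and intervention groups as random rather than fixed effects. Each couple and group belongs to one arm, so fixed effects for them would absorb the condition term in option 1 and cancel the benefit of the common baseline in option 2.

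For physical IPA, rely on the urn factor and do not expect a gain from the baseline score. Keep the unadjusted model as a sensitivity analysis. Socioeconomic status and education are not urn factors and may stay secondary, but the plan should say which analyses they enter.

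The cost is SAP wording and a few extra model terms. The CTS-2, MMEA and DAS are already collected at baseline; whether severity needs anything more depends on its definition.

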AIM 3: To facilitate future implementation of *SAH-C*, we will employ a mixed-methods approach, guided by complementary implementation frameworks, to examine potential barriers, facilitators, and potential for intervention refinement. This aim will be fulfilled by accomplishing the following subaims:

Subaim 3.1: To identify system, facilitator, and dyadic-level barriers and facilitators to implementation.

Subaim 3.2: To assess the acceptability of *SAH-C* among stakeholders in a military setting.

(2) Background and Significance

(a) Background.

Only one experimentally controlled evaluation of IPA intervention effectiveness has been conducted in a military setting. Among a large sample of married Navy couples in which the husband used IPA, Dunford²⁷ found that none of the randomly assigned year-long intervention modalities were effective in reducing IPA at six and 12 months post-intervention. Dunford's²⁷ findings highlighted a need for program modification efforts to meet the needs of military families and also mirrored findings of a lack of program efficacy in civilian settings.²⁸ These data highlight a need for prevention programs focusing on improving intimate relationships and reducing the risk of onset of IPA,²⁹ particularly given that relationship conflict typically serves as a precursor to IPA,³⁰ and more subtle forms of IPA early in relationships are predictive of later violence.³¹

The *SAH-C* intervention is based on a social information processing model of IPA holding that trauma may negatively impact on one's ability to interpret and respond to social situations effectively, and highlights the importance of cognitive behavioral strategies to monitor one's thoughts and responses to difficult interpersonal situations.³² The model derives from prior theory^{33,34} and research indicating that those who use IPA are more likely to exhibit irrational beliefs, problematic thinking, and hostile interpretations of others' intentions.³⁵⁻³⁸ Through the improvement of social information processing, conflict and IPA risk should decrease. Core themes that underlie social information processing and relationship problems, including those related to power and control conflicts, low self-esteem, and trust difficulties are also addressed throughout the program.

(b) Significance.

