Participants (service members and partners) will separately receive remuneration of a \$50 Visa Gift Card or a \$50 check sent to their address for completion of each assessment. Due to military compensation restrictions, and to ensure no conflict, if the service member is active duty, they may only be compensated if they fill out their surveys while on off-duty or on leave status.

(h) Intervention after Completion of Trial

Following the completion of the final assessment, all participants assigned to the *SP* condition will be offered the opportunity to participate in a *SAH-C* group. This participation would be entirely voluntary and would involve no further assessment or remuneration.

(6) Measures

(a) Outcome Measures

Outcome assessments are identical to those from Phase 1, though the assessment window for Phase 2 assessments refers to the prior three months. Data collected will include demographics questionnaire, partner contact form, PCL, AUDIT, Post-Intervention satisfaction, suicidality measure, MMEA⁸⁰, CTS2⁴⁴, ongoing intervention questionnaire, and DAS⁶⁹.

(b) Intervention Compliance Measure

Session Attendance will be measured as the total number of group sessions attended by each client.

(7) Stakeholder Meetings

Stakeholder meetings will be held to discuss study performance and needs of the study, such as discussions related to study recruitment, barriers to participation, and dissemination of research findings.

(c) Intent-to-Treat (ITT) versus “Adequate Dose” Analyses

An ITT philosophy will be strictly adopted. Experts in clinical trials have noted that no consensus exists about how missing data should be handled in ITT analyses, and different imputation approaches result in various potential biases. Thus, there is no single definition of ITT, and the phrase carries different meanings for different researchers.^{87,88} Therefore, every effort will be made to collect complete outcome data for all randomized participants, regardless of their intervention completion. As discussed in section D.3.7., measurement losses are expected to be relatively small due primarily to the use of tracking procedures, as well as the relatively short follow-up assessment periods.

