Analyses will first be conducted on the ITT sample, and then on the subset of participants who are considered to have received an “adequate dose” of the group intervention over the course of the study. We intend to focus on a comparison of those who had an adequate dose versus completed the intervention, because the group sessions will continue in spite of a couple’s non-attendance. This approach is consistent with prior group interventions.⁸⁹ It is recognized that the ITT and adequate dose analyses address different questions, and only the ITT analyses permit strong inferences. However, there is important information to be gained in looking at the data both ways.

(d) Primary Data Analyses

Formal data analyses will be conducted only on those subjects recruited during Phase 2 of the project, as this is the only phase that includes random assignment. Differences between the *SAH-C* groups and *SP* groups on the frequency of physical and psychological IPA and relationship satisfaction (Aim 1) will be examined with random-effects regression models, using Hierarchical Linear Modeling (HLM5).⁹⁰ Random-effects regression models provide more flexibility in modeling missing data than general linear models. They do not require data to be missing completely at random, but only missing at random (that is, the probability of missingness is

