Our first consideration in estimating the necessary sample size for detecting differential change over time in *SAH-C* versus *SP* in terms of IPA incidence was the expected incidence rate of IPA during the follow-up period. Our sample is at high risk for such incidence as defined by the presence of high levels of marital distress. While there is no prospective military data available that directly speaks to such incidence rates, available estimates suggest a 33% one-year prevalence of IPA among trauma exposed service members.⁹³ Conservatively, it would be expected that during the current project, approximately 16% of cases of IPA would emerge (half of the one year prevalence). However, inclusion of only couples with high levels of marital distress will increase this estimated incidence rate. Accordingly, we expect an increase of 10% in the incidence rate. Together, we based power analyses on an estimated 26% one-year incidence rate. Our second consideration involved expected sample attrition. Based on our prior trial and the specific plan for data capture outlined for the project, we estimate that about 15% of participants will provide no follow-up assessment data. However, power analyses were conducted based on the conservative estimate of 20% assessment dropout. Consistent with an ITT approach, regardless of intervention dropout, we will assess participants randomized into the trial. Thus, dropout from measurement versus intervention is of greatest concern. Our third consideration involved expected within-subjects correlations. The within-subjects correlation was estimated as the average correlation observed in our previous trial for pre-intervention, post-intervention, and follow-up data on reports of physical and psychological IPA on the Revised Conflict Tactics Scale (CTS-2).⁴⁴ These correlations ranged from .53 to .90. We also considered the expected intra-class (group) correlation, which was approximately .05. Finally, consistent with recommendations,⁹⁴ we considered the intra-class (dyadic) correlation among couples. We did not incorporate an estimate of such correlations into power analyses because of our proposed use of a composite measure of IPA, which results in a single index of IPA, thereby eliminating intra-dyad correlations. Together, we assumed an intra-class correlation of .38 for power analyses. Our fifth consideration involved the expected effect size of the *SAH-C* relative to *ST*. Our prior work suggested an ITT effect size of $d = 1.01$. A conservative estimate of a mean effect size of $d = .5$ for the *SAH-C* in terms of reduction of IPA incidence was utilized for the power analysis.

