Inclusion criteria are as follows: (a) couples (heterosexual and same-sex dyads) must be in an intimate relationship; (b) participants and their partners must be over the age of 18, due to our emphasis on adult IPA, and so that all participants will be legally able to provide consent without parental involvement; (c) both members of the couple report no occurrence of physical IPA in the past 3 months; (d) at least one member of the couple reports at or below a score of 100 on the Dyadic Adjustment Scale (DAS), a cutoff score used to distinguish relationship distress, or they report the presence of psychological aggression in the past three months; and (e) both members of the couple provide research consent. Pregnant women are eligible to participate in this study. Research indicates that pregnant women may be at increased risk for intimate partner victimization. Thus, violence prevention interventions may be particularly applicable and important for this group. Potential participants will be excluded on the basis of reading difficulties that preclude valid completion of the assessment instruments.

Gender Inclusion

The couples-based interventions studied make it likely that equal numbers of men and women will participate. However, we will make no exclusions related to gender/gender identity, and same-sex couples are also eligible for participation.

Minority Inclusion

Across the study sites, 70% of potential participants are Caucasian, 20% are African American, and 10% are of another ethnicity.

(b) Sources of Materials

Data will be obtained from subjects from self-report measures completed through the online data collection tool, REDCap. Data will not be collected from routine medical care. All data gathered and analyzed will be obtained for this specific study. Study participation will not be documented in participants' electronic medical records.

(c) Potential Risks

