All appropriate service members aged 18 or older, with partners over the age of 18, reporting no occurrence of physical IPA over the prior 3 months in their relationship will be invited with their partners to participate in a screening to determine appropriateness for group intervention and assess study eligibility. Members of the couple will arrive together but be screened separately to ensure confidentiality and safety. Both members of the couple will be administered the DAS to assess relationship distress, partner contact frequency, the MMEA for emotional abuse, the PCL to screen for PTSD, the AUDIT to screen for alcohol use, the CTQ for child abuse and neglect history, the CTS-2 to assess lifetime history of IPA in their current relationship, the suicidality measure, and the demographics questionnaire. If either participant fails to meet study eligibility requirements, the couple's participation will end. If IPA is reported by either partner, the trained psychoeducational facilitator will separately inform them that they are not eligible for this study, and will assess the victim or victims' perceptions of safety, discuss safety planning with the victim(s) (e.g., packing a small bag with a change of clothes and important papers in the event that s/he needs to escape), and will provide them with local contact information for Victim Advocacy services. Victims will be educated by the Victim Advocate about reporting options which include restricted reporting.

In the event a participant endorses suicidal ideation, the facilitator will conduct safety planning and offer a referral to FAP for additional assistance. If there is imminent threat, the facilitator will inform FAP to conduct a formal suicide assessment or accompany the participant to the emergency room. Additionally, if they have a counselor we will direct them to contact their counselor immediately.

(b) Protection Against Risk

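### For physical IPA, couples with no follow-up data enter the primary model with only a baseline of zero, so the missing-at-random rationale covers them only within arm; baseline severity should be brought into the analysis

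*Combined protocol and SAP*

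**What the plan says.** Section (d) Primary Data Analyses chooses random-effects regression partly for its handling of missing data: "They do not require data to be missing completely at random, but only missing at random". It explains that missingness is "assumed to be a function of observed covariates and previously measured outcomes, but not unobserved outcomes". The terms named for the primary model are condition, time, and intervention group, couple and perhaps site. The effect of interest is the intervention-by-time interaction. Socioeconomic status and education are the only covariates named, and "these will be included in follow-up analyses to significantly reduce error variance". No baseline severity measure is named, although (5)(b) Assignment to Groups balances the urn randomization on case severity.

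For physical IPA, the inclusion criteria require that "both members of the couple report no occurrence of physical IPA in the past 3 months", and (6)(a) Outcome Measures states that "the assessment window for Phase 2 assessments refers to the prior three months". The two windows coincide, so the baseline score is zero by design. On losses, (g) Power Analysis says "we estimate that about 15% of participants will provide no follow-up assessment data" and then uses 20% as a conservative figure; (5)(g) Attrition plans for 12%.

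**The concern.** A likelihood-based model makes dropout ignorable given the variables it contains, not given everything the trial measured. For psychological IPA and the DAS, a couple with only a baseline record still tells the model something, because the baseline varies and correlates with follow-up. For physical IPA that record is the same constant for every couple, and no covariate distinguishes one couple from another. The rationale based on earlier outcomes and covariates therefore does not reach couples with no follow-up. Their loss is ignorable only if it is random within arm (and within the group and site terms).

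This matters because physical IPA is named in the primary hypotheses, and (2)(a) Background itself states that "more subtle forms of IPA early in relationships are predictive of later violence". Baseline psychological aggression is thus a likely predictor of the outcome, is measured in everyone, and is left out of this model. If it also relates to dropout, and does so differently in the two arms, the contrast is biased in a direction that depends on which arm loses the more severe couples.

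**Working it through.** **Plan's own figure.** The plan gives no figure for bias. Its nearest figure is power above .9. With 280 individuals less 20%, 112 per arm, d = .5: Φ(.5·√(112/2) − 1.96) = Φ(1.78) = .963, which agrees when individuals are counted separately. The point here does not rest on that figure.

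**Step 1: does a baseline-only couple contribute?** A random-intercept model was fitted to simulated data (continuous outcome, three follow-ups, true contrast −0.50, about 20% of couples with no follow-up, severity driving dropout in SP only). With an all-zero baseline the contrast was −0.325 with the no-follow-up couples and −0.325 without them, equal to the raw difference in observed means. With a varying baseline the model gave −0.471.

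**Step 2: when does bias arise?** Take two equal-sized severity strata with assumed control incidence 42% and 10% (mean 26%).
- Dropout 30%/10% in both arms: observed control incidence (.70×.42 + .90×.10)/1.60 = .240. With no effect both arms give .240, so bias is 0. With an additive effect bias is also 0. With a constant relative effect (true −13.5 points) the observed difference is .240×(13.5/26) = 12.5 points, a bias of 1.0 point.
- Dropout 35%/5% in SP only, no true effect: (.65×.42 + .95×.10)/1.60 = .230, so SAH-C looks 3.0 points worse. The same dropout in SAH-C only makes it look 3.0 points better.

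**Step 3: size under stated assumptions.** From the plan: SP incidence 26%, d = .5, loss 15% or 20%. Assumed: d is on the log-odds scale; severity Z is standard normal; the odds ratio is 2 per SD of Z for both incidence and dropout.
- SAH-C incidence: odds ratio exp(−.5·π/√3) = .404; odds .26/.74 × .404 = .142; incidence .142/1.142 = 12.4%. True difference 26.0 − 12.4 = 13.6 points.
- With logistic incidence p(Z) and dropout q(Z), intercepts solved for these margins, observed incidence is E[p(Z)(1 − q(Z))]/E[1 − q(Z)]. At 15% severity-driven loss this gives 24.7% in SP and 11.6% in SAH-C; at 20%, 24.3% and 11.4%. An arm whose loss is unrelated to severity keeps 26.0% or 12.4%.

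| Severity drives dropout in | 15% loss per arm | 20% loss per arm |
|---|---|---|
| SP only | 24.7 − 12.4 = 12.3 | 24.3 − 12.4 = 11.9 |
| Both arms | 24.7 − 11.6 = 13.1 | 24.3 − 11.4 = 12.9 |
| SAH-C only | 26.0 − 11.6 = 14.4 | 26.0 − 11.4 = 14.6 |

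With no true effect and 20% loss, the one-arm cases give a spurious 26.0 − 24.3 = 1.7 points in either direction; the both-arms case gives 0. Over odds ratios 1.5 to 3 at 20% loss, SP-only runs from 13.0 down to 10.0 and SAH-C-only from 13.9 up to 15.9.

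**Step 4: does baseline severity repair it?** In the set-up of Step 1 with an all-zero baseline, averaged over repeated simulations, the planned model gave −0.48 (both arms; Monte Carlo standard error 0.017), −0.31 (SP only) and −0.68 (SAH-C only). Adding severity by time gave −0.50, −0.50 and −0.49. The covariate there was the true driver of dropout, so a real, imperfect measure would remove only part of the bias.

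**The case against.** Several objections stand, and they limit the point.

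- **Later dropouts are covered.** A reader might infer that missing at random fails altogether for physical IPA, or that all losses must be missing completely at random. Neither follows. Three post-baseline assessments are planned; a couple with post-intervention data who leaves later has an informative earlier outcome in the model, which also conditions on arm.
- **Severity-driven dropout alone does not bias the contrast.** With equal loss and slope in both arms, bias is zero under a null or additive effect, and in the table above it is at most 0.7 points (13.6 − 12.9).
- **The prior trial does not show a large bias.** Its Table 1 counts fall from 41 to 31 (24% lost) and from 37 to 18 (51% lost). Used directly, with severity driving SP dropout only, those losses would give an observed 9.7 points. But they are losses by the six-month visit. They do not show how many couples gave no follow-up, nor that severity was the reason. They serve only as an upper scenario.
- **Nor do couples without follow-up make up most of a 20% loss.** In (g) the 20% is a conservative substitute for the 15% estimate, not a total that contains it.
- **The drivers are assumed.** No document gives a relation between severity and dropout. The background statement concerns later violence. Step 3 also uses a binary outcome at one visit, whereas the plan models frequency over repeated visits.
- **The plan limits the exposure.** It follows participants who are terminated early and commits to complete outcome collection. That reduces the number of couples concerned but does not say how those who remain missing are handled.

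One further reservation: the zero baseline follows from eligibility, but the screening section uses "the CTS-2 to assess lifetime history of IPA in their current relationship", and the prior trial had a non-zero Veteran mean at T1 (.44) despite excluding Veteran physical IPA. The baseline window is therefore not fully settled.

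**Conclusion.** The point holds in a limited form. For physical IPA, the roughly 15% of couples expected to give no follow-up (21 of 140 if losses fall by couple) add nothing to the planned contrast, and the stated rationale amounts for them to missing at random within arm. Bias is conditional: it needs severity-related dropout that differs by arm in slope or amount, or an effect that varies with severity. Under the assumed odds ratio of 2, the distortion of a true 13.6 points is 0.5 to 1.3 points at 15% loss and 0.7 to 1.7 points at 20%, toward or away from the null. At 20% loss the one-arm cases span 10.0 to 15.9 points over odds ratios 1.5 to 3. The documents do not establish that such dropout will occur. The gap is worth closing because its direction cannot be assumed conservative and the data that would reduce it are already collected.

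**What to change.** In section (d), for physical IPA:

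1. Include baseline severity measures already collected (CTS-2 psychological score or MMEA, DAS, and the urn severity factor, which should be named) with their interaction with time. The interaction carries the adjustment, since the outcome is zero for everyone at baseline. Alternatively, impute missing follow-ups within condition from these baselines, so that couples without follow-up are represented; this version also allows the effect to vary with severity.
2. Keep the covariate-free model as a sensitivity analysis.
3. Reword the missing-at-random sentence to name the variables it conditions on for each outcome.
4. State the recall window of the baseline CTS-2 used in the analysis and reconcile it with the lifetime window in the screening section.

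The cost is plan wording and a modest amount of extra analysis, with no new data. The standard error may rise slightly. Dropout that depends on unmeasured factors would remain.
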